5.1.3 Exploratory Endpoint(s)

Exploratory Endpoints:

- ORR, TTR, DOR, PFS, DCR, and CBR according to RECIST 1.1
- Assess overall survival (OS)
- Explore the pharmacodynamic effect of E7046 on selected immune cell populations and selected biomarkers in tumor infiltrate and in peripheral blood
- Explore 18FDG-PET as a biomarker of response
- Explore the pharmacokinetic/pharmacodynamic (PK/PD) relationship

5.2 STUDY SUBJECTS

5.2.1 Definitions of Analysis Sets

Full Analysis Set will include all subjects who received at least one dose of study drug. This will be the primary analysis set for efficacy evaluations, as well as for demographic and baseline characteristics. This analysis set will also constitute the **Safety Analysis Set**.

DLT Evaluable Set will consist of those subjects who are evaluable for the DLTs (Section 13.3). This will be the analysis set for DLT analysis.

Pharmacokinetic (PK) Analysis Set will include all subjects who have received at least one dose of study drug and have at least one evaluable plasma concentration.

Pharmacodynamic (PD) Analysis Set will include all subjects who have received at least 1 dose of study drug and have evaluable pharmacodynamic data.

Pharmacokinetic/Pharmacodynamic (PK/PD) Analysis Set will consist of all subjects in the Safety Analysis Set that also have evaluable serum PK and PD pretreatment assessment and at least 1 post treatment assessment.

Response Evaluable Set will consist of those subjects who have received at least 1 dose of study drug and have measurable disease at baseline and at least 1 post-baseline evaluation. This will be the primary analysis set for tumor response analysis.

FDG-PET Analysis Set will include all subjects with a baseline and at least one post baseline evaluable FDG-PET/CT assessment.

5.2.2 Subject Disposition

The number (percentage) of treated subjects will be summarized as well as subjects who completed the study/discontinued from the study and reasons for discontinuation by dose group.

The number (percentage) of subjects who completed the study treatment/discontinued from the study treatment and reasons for discontinuation will also be summarized by dose group.

The number of subjects who signed informed consent and the number (percentage) of subjects who failed screening and the reasons for screen failure will be summarized, based on data reported on the Screening Disposition Case Report Forms (CRFs). Reasons for screen failure will also be listed.

5.2.3 Protocol Deviations

Protocol deviations are based on the selected inclusion, exclusion, and on-treatment criteria.

The major and minor protocol deviations will be finalized, documented and listed prior to database lock.

5.2.4 Demographic and Other Baseline Characteristics

The demographic and baseline characteristics will be summarized using descriptive statistics by dose group. Subject demography information will be collected at the Screening Visit.

Demographic and other baseline characteristics will be summarized using the Full Analysis Set, for each dose group and listed for each subject. For continuous demographic/baseline variables including age (year), height (cm), weight (kg), BMI (kg/m^2 : $\text{weight}[\text{kg}]/\{\text{height}[\text{m}]\times\text{height}[\text{m}]\}$), and BSA (m^2 : $\text{height}[\text{cm}]\times\text{weight}[\text{kg}]/3600$), results will be summarized and presented as n, mean, standard deviation, median, 25% percentile (Q1), 75% percentile (Q3), minimum and maximum values. For categorical variables, the number and percentage of subjects will be used. Categorical variables include age group (≤ 65 , > 65 years), race (White, Black or African American, Asian [Japanese, Chinese, Other Asian], American Indian or Alaska Native, Native Hawaiian or other Pacific Islander, and Other), ethnicity (Hispanic or Latino, not Hispanic or Latino), and Eastern Cooperative Oncology Group (ECOG) performance status grade (0 - 5).

MEDICAL HISTORY

The number (percentage) of subjects reporting a history of any medical condition, as recorded on the Case Report Form (CRF), will be summarized for each dose group and overall. A subject data listing of medical and surgical history will be provided.

5.2.5 Prior and Concomitant Therapy

All investigator terms for medications recorded on the CRF will be coded using the World Health Organization (WHO, Geneva, Switzerland) Drug Dictionary using the March 2015 version or later. The number (percentage) of subjects who have taken prior and concomitant medications will be summarized on the Full Analysis Set, by Anatomical Therapeutic Chemical (ATC) Classification and WHO drug preferred term. Prior medications will be defined as medications that stopped prior to the first dose of study drug. Concomitant medications will be defined as medications that (i) have started before the first dose of study drug and are continuing at the time of the first dose of study drug, or (ii) have started on or after the date of the first dose of study drug up to 30 days following the last dose.

A medication that cannot be determined as prior/concomitant due to missing/incomplete dates will be regarded as a concomitant medication.

Prior and concomitant medications will be summarized separately by anatomic class, pharmacological class, and WHO drug name (preferred term) by frequency counts and percentages.

Subject data listings will be provided for medications recorded during the study.

5.3 DATA ANALYSIS GENERAL CONSIDERATIONS

5.3.1 Pooling of Centers

Subjects from all centers will be pooled for all analyses.

5.3.2 Adjustments for Covariates

Not applicable.

5.3.3 Multiple Comparisons/Multiplicity

Not applicable.

5.3.4 Examination of Subgroups

No subgroup analyses are planned for this study.

5.3.5 Handling of Missing Data, Drop-outs, and Outliers

Adverse Events

An adverse event is defined as “treatment emergent” if it starts on or after the first dose date.

Adverse events with incomplete start dates will be considered treatment emergent if:

- a. Date is completely missing; or
- b. Year is missing; or
- c. Day and month are missing and the year is equal to or after the year of the first dose date; or
- d. Day is missing, and
 - the year is after the year of the first dose; or
 - the year is equal to the year of the first dose date and the month is equal to or after the month of the first dose date.

Concomitant Medications

Concomitant medications will be defined as medications that (1) started before the first dose of study drug and were continuing at the time of the first dose of study drug, or (2) started on or after the date of the first dose of study drug up to 30 days after the subject’s last dose.

Unless a medication is prior determined by the end date (i.e., end date is before the first dose) regardless the start date is partially or completely missing, medications with incomplete start and/or end date will be considered concomitant if:

- a. Date is completely missing; or
- b. Year is missing; or
- c. Day and month are missing and the year is equal to or after the year of the first dose date; or
- d. Day is missing, and
 - the year is after the year of the first dose; or
 - the year is equal to the year of the first dose date and the month is equal to or after the month of the first dose date.

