### 9.5.8 Reporting of Serious Adverse Events, Pregnancy, and Events Associated with Special Situations

#### 9.5.8.1 Reporting of Serious Adverse Events

**All SERIOUS ADVERSE EVENTS, regardless of their relationship to study treatment, must be reported on a completed SAE form by email or fax as soon as possible but no later than 24 hours from when the investigator becomes aware of the event.**

Serious adverse events, regardless of causality assessment, must be collected through the last visit and for 30 days after the subject's last dose. All SAEs must be followed to resolution or, if resolution is unlikely, to stabilization. Any SAE judged by the investigator to be related to the study treatment or any protocol-required procedure should be reported to the sponsor regardless of the length of time that has passed since study completion.

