#### 9.7.1.10.2 ADVERSE EVENTS

The AE verbatim descriptions (investigator terms from the CRF) will be classified into standardized medical terminology using the Medical Dictionary for Regulatory Activities (MedDRA). Adverse events will be coded to the MedDRA (Version 18.0 or higher) lower level term (LLT) closest to the verbatim term. Adverse events will be presented by MedDRA preferred term (PT) nested within primary system organ class (SOC).

A TEAE is defined as an AE that emerges during treatment, having been absent at pretreatment (Baseline), or

- Reemerges during treatment, having been present at pretreatment (Baseline) but stopped before treatment, or
- Worsens in severity during treatment relative to the pretreatment state, when the AE is continuous.

Only those AEs that were treatment emergent will be included in summary tables. All AEs, treatment-emergent or otherwise, will be presented in subject data listings.

The TEAEs will be summarized by treatment cohort. The incidence of TEAEs will be reported as the number (percentage) of subjects with TEAEs by SOC and PT. A subject will be counted only once within a SOC and PT, even if the subject experienced more than 1 TEAE within a specific SOC and PT. The number (percentage) of subjects with TEAEs will also be summarized by maximum severity (mild, moderate, or severe) and by relationship to study drug (Yes [related] and No [not related]), respectively.

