5.6.3 Adverse Events

The adverse event verbatim descriptions (investigator terms from the eCRF) will be classified into standardized medical terminology using the Medical Dictionary for Regulatory Activities (MedDRA) version 18.0 or later. Adverse events will be coded to primary System Organ Class (SOC) and preferred term (PT) using MedDRA.

A treatment-emergent AE (TEAE) is defined as an AE that emerged during treatment (from first dose to 30 days after last dose of study drug) and

- had been absent at pretreatment (Baseline) or
- reemerged during treatment, having been present at pretreatment (Baseline) but stopped before treatment, or
- worsened in severity during treatment relative to the pretreatment state, when the AE was continuous.

Only those AEs that are treatment emergent will be included in summary tables. All AEs, treatment emergent or otherwise, will be presented in subject data listings.

The incidence of TEAEs will be reported as the number (percentage) of subjects with TEAEs within SOC and PT. Subjects will be counted only once within a SOC and PT, even if the subject experienced more than one TEAE within a specific SOC and PT, and the subject will be counted with the worst grade for that particular AE. The number (percentage) of subjects with TEAEs will also be summarized by highest Common Terminology Criteria for Adverse Events (CTCAE) grade. The number (percentage) of subjects with treatment-related TEAEs will also be summarized by SOC and PT. Treatment-related TEAEs include those events considered by the investigator to be possibly or probably related to study treatment. In summary, the following TEAE tables will be provided:

- Overview of TEAEs
- TEAEs by SOC and PT
- TEAEs by SOC, PT, and CTCAE grade
- TEAEs with CTCAE grade 3 or 4 by SOC and PT
- TEAEs that led to drug discontinuation by SOC and PT
- TEAEs that led to dose reduction by SOC and PT
- TEAEs that led to dose interruption by SOC and PT
- Treatment-related TEAEs by SOC and PT
- Treatment-related TEAEs with CTCAE grade 3 or 4 by SOC and PT
- Treatment-emergent serious AEs by SOC and PT
- Treatment-related treatment-emergent serious AEs by SOC and PT

Subjects AE listings (treatment emergent or not) will be provided. In addition, the following subject AE listings will be provided:

- All fatal adverse events.
- All non-fatal serious adverse events (SAEs)
- All non-fatal non-serious treatment-emergent adverse events that led to discontinuation of treatment

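### SAP 5.3.5 defines a treatment-emergent AE differently from 5.6.3, and its partial-date rule can count AEs that ended before the first dose

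*SAP*

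**What the plan says.** The AE part of SAP 5.3.5 (missing data) opens with a complete sentence of definition: an AE is treatment emergent "if it starts on or after the first dose date". Four rules, a to d, follow under the lead-in "Adverse events with incomplete start dates will be considered treatment emergent if". They look only at what is known of the start date. A wholly missing date or a missing year counts as treatment emergent. So does a year-only date in or after the year of first dose, and a month-and-year date in or after the month of first dose.

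The medication rule in the same section has almost the same four conditions, but it begins with an exception: "Unless a medication is prior determined by the end date (i.e., end date is before the first dose". The AE rule has no such clause.

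SAP 5.6.3 (adverse events) defines a TEAE as one that "emerged during treatment (from first dose to 30 days after last dose of study drug" and that was absent at baseline, re-emerged, or "worsened in severity during treatment relative to the pretreatment state, when the AE was continuous". Protocol 9.7.1.10.2 has the same three routes, including "Worsens in severity during treatment relative to the pretreatment state, when the AE is continuous", but states no 30-day limit. Neither SAP section refers to the other.

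Section 5.6.3 also says: "Only those AEs that are treatment emergent will be included in summary tables". Safety and tolerability is a primary endpoint (SAP 5.1.1).

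**The concern.** The 5.3.5 sentence reads as a definition in its own right, not as a date-imputation convention, and it departs from 5.6.3 at both ends. At the early end it has no route for a pre-existing AE that worsens on drug. At the late end it has no cut-off after last dose. Its lack of a worsening route also departs from the protocol.

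The partial-date rule is a second and independent defect. Pre-dose AEs will be in the database: collection starts at consent (Protocol 9.5.5.1), and consent may be signed up to 8 weeks before first dose (Protocol Table 6, footnote a). An AE from that period with an incomplete start date and a known pre-dose end date would be tabulated as treatment emergent.

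At stake is the content of the TEAE tables, which are the main summary of a primary endpoint in cohorts of six.

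**Working it through.** The plan states no figure to reproduce here, so the check sets the rules side by side on test records. The example assumes first dose on day 0 and last dose on day 84.

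| Test record | 5.3.5 sentence | 5.6.3 |
|---|---|---|
| New onset on day 10 | yes | yes |
| Re-emerged as a new record on day 15 | yes | yes |
| Pre-existing and stable, from day -20 | no | no |
| One continuous record from day -20, worsens on day 10 | **no** | **yes** |
| Onset on day 129 (last dose + 45) | **yes** | **no** |

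The two texts agree on ordinary events and split on exactly two kinds of record.

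**Partial-date rules, under either definition.** Section 5.6.3 has no rule for incomplete dates, so rules a to d are the only ones available.

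- Start date wholly missing, end on day -5: treatment emergent by rule a. A missing year gives the same result by rule b.
- Only the start year known, equal to the year of first dose, AE ended before dosing: treatment emergent by rule c.
- First dose on the 20th, start known only to that month, AE ended on the 10th: treatment emergent by rule d.

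None of these events can have emerged on treatment, so the rules return an answer that 5.6.3 itself would reject. Rules c and d also have no upper limit: a partial start date that clearly falls more than 30 days after last dose is still counted.

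**Size per subject.** The change in a by-dose percentage when one subject is reclassified is 100/n:

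- n = 6 (escalation cohort): 100/6 = 16.7 points
- n = 16 (largest expansion cohort): 100/16 = 6.25 points
- n = 40 (whole study): 100/40 = 2.5 points

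This holds only if the subject has no other qualifying event in the same table cell.

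**Chance that a cohort is affected.** The documents give no rate. As an assumption, let each subject independently have probability p of an affected record. The chance of at least one among six is 1 - (1 - p)^6:

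- p = 0.02: 1 - 0.98^6 = 0.114
- p = 0.05: 1 - 0.95^6 = 0.265
- p = 0.10: 1 - 0.90^6 = 0.469
- p = 0.20: 1 - 0.80^6 = 0.738

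The range of 11% to 74% only shows how strongly the answer depends on an unknown p. It is not an estimate for this trial.

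**The case against.** The strongest reply is that the governing text is reasonably clear. Section 5.3.5 concerns missing data and its sentence introduces date rules. Section 5.6.3 is the AE analysis section, gives the full definition and lists the tables. SAP section 8 sends the reader to the endpoint discussions for more specific detail, and the protocol agrees with 5.6.3 on re-emergence and worsening. SAP section 7 disclaims any change to the planned analysis, although it cites an earlier protocol version than SAP section 3 does. This largely stands. A reader might infer that the primary safety tables turn on which section is programmed; the documents do not support that, and separate programming specifications (SAP section 9) may settle the matter. What remains is that the SAP itself carries a contradictory sentence.

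A reader might also infer that worsening of baseline symptoms will be lost. That does not follow. Protocol 9.5.5 requires all grades to be recorded, rising and falling, and 9.5.5.1 counts an exacerbation of an existing disease as an AE. If a worsening is entered with its own start date, both definitions capture it. Only a single continuous record that keeps its pre-dose start date is exposed, and the documents do not say how the CRF handles this. Worsening of the cancer itself goes to efficacy as progression.

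A third inference is that late events are certainly in the data, because related SAEs "should be reported to the sponsor regardless of the length of time that has passed since study completion" (Protocol 9.5.8.1). That sentence governs reporting to the sponsor. It does not show that such events enter the locked database, and routine AE collection runs only through the last visit and for 30 days after last dose.

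On the end-date gap, it is fair to say that it over-includes rather than hides events, that every AE is listed regardless, and that rules c and d already leave out start years or months known to precede first dose. These points limit its size. They do not answer the defect, because the rule as written gives a wrong classification and the neighbouring medication rule shows the intended safeguard.

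**Conclusion.** Both defects are on the page and should be corrected before database lock. They are separate: the first is a conflict of definitions in which 5.6.3 probably prevails, while the second misclassifies whichever definition is used.

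The consequence is limited to the descriptive TEAE tables. DLTs are determined subject by subject in a separate review (SAP 5.6.2), so the DLT rule and the MTD do not change. How often a record would be affected cannot be computed from the documents. It depends on how worsening is recorded on the CRF, on whether late events reach the database, and on how many AEs have incomplete start dates. The one firm number is conditional: 16.7 points in a cohort of six for each reclassified subject with no other qualifying event in that cell.

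**What to change.** Replace the first AE sentence of SAP 5.3.5 with: *Treatment-emergent is defined in 5.6.3; the rules below apply only to incomplete start dates.*

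Add to the lead-in of rules a to d: *unless the AE end date is before the first dose date, or the known part of the start date shows onset more than 30 days after last dose.*

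The cost is two lines of SAP text, with the programming specifications checked against them. No data collection changes.

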5.3.6 Other Considerations

There are no other specific considerations that are not covered in other relevant sections of this SAP.

5.4 EFFICACY ANALYSES

Tumor response will be assessed by both immune-related RECIST [irRECIST] and modified version of RECIST 1.1 criteria [Eisenhauer, 2009]. All efficacy analyses will be performed on the Response Evaluable Set.

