### 9.1.3.3 Extension Phase

The Extension Phase consists of 2 periods:

- **Treatment Continuation Period**, during which subjects will continue in Cycle 2 and beyond to receive the same treatment they received during the Treatment Phase.  
The **Treatment Continuation** period will start at the end of the Treatment Phase and will end with the completion of the Off-Treatment Visit (which will occur within 30 days after the last administration of the study drug). It consists of study drug treatment on a 21-day cycle, regardless of dose interruptions. Subjects will undergo safety and efficacy assessments as defined in Schedule of Procedures ([Section 9.5.6.1](#)) . Subjects will discontinue the study drug and become Off-Treatment at the time of disease progression, development of unacceptable toxicity, withdrawal of consent or termination of the study program.
- A **Follow-Up Period**, for study assessments after discontinuation from study treatment.  
The **Follow-up Period** will begin the day after the Off-Treatment Visit and will continue as long as the study subject is alive until the completion of the primary analysis, unless the subject withdraws consent or until the sponsor terminates the study. Subjects, who discontinue study treatment without disease progression will continue to be followed and undergo tumor assessments every 6 weeks until disease progression or until the start of another anticancer treatment. In the follow-up period, subjects will be treated by the investigator according to the prevailing local standard of care. Subjects will be followed every 12 weeks ( $\pm 1$  week) for survival, performance status and subsequent anticancer treatments. The sponsor may decide to terminate survival follow-up anytime during the Extension Phase or when all subjects have discontinued study treatment.

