- t. A bone scan (99m-technetium polyphosphonate scintigraphy, whole body bone MRI, or 18F-NaF) to assess bone metastases will be performed within 6 weeks prior to C1D1 and then every 24 weeks (within that 24th week) from C1D1 for tumor types known to metastasize to bone (eg TNBC, NSCLC, RCC.), or sooner if clinically indicated. In subjects whose body CT/MRI scans indicate irCR has been achieved, a bone scan will be required at confirmation of irCR to exclude new bone metastases. The same methodology and acquisition techniques used at screening should be used throughout the study to ensure comparability. If a non-target lesion is being followed by bone scan (not present on CT/MRI), and is not imaged at a follow-up time point because a bone scan is not required at that time point, the time point non-target lesion response will be based upon the other non-target lesions and will not be considered not evaluable (NE).
- u. E7046 should be taken daily at the dose assigned, with fasting 2 hours before and 2 hours after ingestion of E7046 capsules. On visit days, subjects should not take study medication before evaluations are performed.
- v. Adverse events and prior and concomitant medications information to be collected at every study visit.
- w. Subjects who discontinue study will be followed for survival. Survival follow-up will be conducted approximately every 12 weeks on all subjects, unless they withdraw consent. Follow up on subsequent treatment and clinical response will be collected.

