#### 9.7.1.2 Definitions of Analysis Sets

**Full Analysis Set** will include all subjects who received at least one dose of study drug. This will be the primary analysis set for efficacy evaluations, as well as for demographic and baseline characteristics. This analysis set will also constitute the **Safety Analysis Set**.

**DLT Evaluatable Set** will consist of those subjects who are evaluable for the DLTs ([Section 9.1.1.2](#)). This will be the analysis set for DLT analysis.

**Pharmacokinetic (PK) Analysis Set** will include all subjects who have received at least one dose of study drug and have at least one evaluable plasma concentration.

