|---------------------------------|--|--|
| irCR | irCR | irCR |
| irCR | irPR/irSD/irPD | irSD/irPR* |
| irPR | irPR/irCR | irPR |
| irPR | irSD | irSD |
| irPR | irPD | irSD |
| irSD | irSD | irSD |
| irSD | irPD | irSD, provided minimum irSD duration met |
| irPD | irPD | irPD |

*If an irCR is truly met at first time point, then any disease seen at a subsequent time point, even disease meeting irPR criteria relative to baseline, makes the disease irPD at that point (since disease must have reappeared after irCR). Best response would be irSD. However, sometimes 'irCR' may be claimed when subsequent scans suggest small lesions were likely still present and in fact the patient had irPR, not irCR at the first time point. Under these circumstances, the original irCR should be changed to irPR and the best response is irPR.

- **irNE**

The BOR will be irNE in the following scenarios:

- No evaluable tumor assessment
- Only one evaluable tumor assessment with the result of either irPD or irCR/irPR/irSD but the duration of irSD is less than 5 weeks.

- **Handling of Missing /Not Evaluable Tumor Assessments**

The following rules will be used to handle missing and/or not evaluable tumor assessments:

- One missing or not evaluable tumor assessment will be ignored if it is between two evaluable tumor assessments.
- All the missing and/or not evaluable tumor assessments will be ignored if they are the only ones in between two irPDs. In this case, the irPD is confirmed and the documented start date of irPD is the date of the first irPD.
- All the missing and/or not evaluable tumor assessments will be ignored if there is no evaluable tumor assessment after them.
- Two irCRs, two irPR, or irPR and irCR with two or more missing and/or not evaluable tumor assessments in between will result in not evaluable result, i.e., irNE.

Objective Response Rate (ORR)

The objective response rate (ORR) is the proportion of patients achieving a best overall response of confirmed irPR or irCR according to irRECIST from first dose date until disease progression, death, or end of study (whichever occurs first). Subjects who do not have a tumor response assessment for any reason will be considered nonresponders and will be included in the denominator when calculating the response rate. The count and percentage for the ORR will be summarized by dose group.

Time to Response (TTR)

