The time to response (TTR) is defined as the elapsed time (weeks) from the first dose date to the documented start date of confirmed irCR/irPR according to irRECIST. The descriptive statistics for the TTR will be summarized by dose group for the patients with the BOR of confirmed irCR/irPR.

Duration of Response (DOR)

The duration of response (DOR) is defined as the time (months) from the documented start date of confirmed irCR/irPR according to irRECIST until the documented start date of irPD or death (whichever occurs first).

For subjects with the BOR of irCR/irPR who did not die and had no documented progression before the cut-off date for the end of the study, or before early discontinuation (including discontinuations due to toxicity, undocumented clinical progression, change of cancer treatment, or decreasing performance status), and who died or progressed after more than one missed visit, will be censored on the date of their last assessment with the BOR of irCR, irPR or irSD.

The descriptive statistics (median and its standard error, Q1 and Q3) for the DOR will be summarized by dose group for the patients with the BOR of confirmed irCR/irPR using Kaplan-Meier method.

Progression-Free Survival (PFS)

Progression-free survival is defined as alive without confirmed irPD using irRECIST at the end of study or certain evaluation time points such as 3 months, 6 months, etc. The time for PFS is defined as the elapsed time from first dose date to the documented start date of irPD or death (whichever occurs first).

In analysis of PFS, the censoring rule is as follows:

- Subjects who did not die and had no documented progression (confirmed irPD) before the cut-off date for the end of the study, or before early discontinuation (including discontinuations due to toxicity, undocumented clinical progression, change of cancer treatment, or decreasing performance status), PFS will be censored on the date of their last evaluable assessment.
- Subjects who died or progressed after more than one missed visit, or non-evaluable assessment, or a combination of two, PFS will be censored on the date of their last evaluable assessment before the death or progression.

The rate for PFS will be summarized by evaluation time point and dose group. The time curve and median of PFS will be estimated and reported by the Kaplan-Meier method.

Disease Control Rate (DCR)

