7 CHANGES IN THE PLANNED ANALYSES

This SAP is in accordance with Clinical Study Protocol v1.0, dated 07 May 2015. No changes to the planned analysis will be applied in this SAP.

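### SAP 5.4 runs every efficacy analysis, including PFS and OS, on the Response Evaluable Set, although both documents name the Full Analysis Set as primary for efficacy and SAP 7 declares no change

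*SAP*

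**What the plan says.** Protocol 9.7.1.2 defines the Full Analysis Set as every subject who took at least one dose and says of it: "This will be the primary analysis set for efficacy evaluations, as well as for demographic and baseline characteristics". SAP 5.2.1 repeats that sentence. The protocol defines no Response Evaluable Set.

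SAP 5.2.1 adds one. Its members must have been dosed and must "have measurable disease at baseline and at least 1 post-baseline evaluation. This will be the primary analysis set for tumor response analysis".

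SAP 5.4 then states: "All efficacy analyses will be performed on the Response Evaluable Set". The irRECIST endpoints (5.4.1, including PFS), the modified RECIST 1.1 endpoints (5.4.2) and OS (5.4.3) all fall under that sentence, and none names a different set.

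For ORR, SAP 5.4.1 says: "Subjects who do not have a tumor response assessment for any reason will be considered nonresponders and will be included in the denominator". Protocol 9.7.1.1 and SAP 5.1.2 carry the same rule. SAP 7 states: "No changes to the planned analysis will be applied in this SAP".

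**The concern.** SAP 5.2.1 and SAP 5.4 give incompatible instructions for the efficacy tables, and following 5.4 departs from the protocol without saying so.

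Membership of the Response Evaluable Set depends on events after treatment starts. A dosed subject who dies early, withdraws consent, starts another therapy or deteriorates without a scan disappears from the analysis. Response rates then rise because the denominator shrinks. PFS loses any deaths that came before a first scan. OS needs no scan at all, yet it would be estimated only in subjects who had an evaluation.

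**Working it through.** No figure in the documents is at issue. The check is a comparison of texts, followed by illustrations of size.

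**Step 1: which condition excludes subjects.** Measurable disease is already required by inclusion criterion 8 (protocol 9.3.1), so the post-baseline evaluation condition does the work. The first scheduled scan is at Week 6 (protocol 9.5.2). Stopping for toxicity does not by itself exclude anyone: under protocol 9.1.3.3, subjects who stop without progression "will continue to be followed and undergo tumor assessments every 6 weeks until disease progression or until the start of another anticancer treatment".

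**Step 2: the ORR rule against the set.** The rule keeps unassessed subjects in the denominator, while the set removes them beforehand. Only subjects whose post-baseline scans were all non-evaluable could remain for the rule to act on.

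**Step 3: OS.** Protocol Table 6, note w, says: "Survival follow-up will be conducted approximately every 12 weeks on all subjects, unless they withdraw consent". Survival data on excluded subjects would therefore be collected and then left out.

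**Step 4: size.** All counts below are assumptions, except the maximum of 40 subjects and the cohort size of 6.

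*Response rates.* SAP 5.4.1 assigns irNE to a subject with no evaluable tumor assessment, so dropped subjects cannot be in the numerator of ORR, DCR or CBR. With m dropped of N, each rate is multiplied by N/(N − m):
- N = 40: 40/38 = 1.05, 40/36 = 1.11 and 40/32 = 1.25 for m = 2, 4 and 8.
- Cohort of 6 with one responder: 1/6 = 16.7% becomes 1/5 = 20% (m = 1) or 1/4 = 25% (m = 2).

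*PFS.* Take N = 40, 8 dropped, and 24-week PFS of 30% in the other 32. Where no progression is documented, "PFS will be censored on the date of their last evaluable assessment"; a subject with no such assessment contributes about zero follow-up. Let d of the 8 have died before a first scan, ahead of any event or censoring in the 32. The Kaplan–Meier estimate on the Full Analysis Set is 32/(32 + d) × 0.30:
- d = 0: 30.0%
- d = 4: 32/36 × 0.30 = 26.7%
- d = 8: 32/40 × 0.30 = 24.0%

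*OS.* Take N = 40, 8 dropped, and 20 of the other 32 alive at 24 weeks. SAP 5.4 reports 20/32 = 62.5%. With all 40 followed and d of the 8 dead by then, the Full Analysis Set value is (20 + 8 − d)/40:

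| d | Full Analysis Set OS |
|---|---|
| 8 | 50% |
| 6 | 55% |
| 4 | 60% |
| 3 | 62.5% |
| 0 | 70% |

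The reported OS is too high only when more than 3 of the 8 died.

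*OS under a survival model.* Suppose OS is exponential and only subjects who die before Week 6 are excluded. With median M weeks, the excluded share is 1 − 2^(−6/M). Twelve-week OS is 2^(−12/M) on the Full Analysis Set and 2^(−6/M) on the Response Evaluable Set.
- M = 13: 27% excluded; 53% becomes 73%.
- M = 26: 15% excluded; 73% becomes 85%.
- M = 52: 8% excluded; 85% becomes 92%.

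In this model the median rises by 6 weeks in each case.

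**The case against.** - **SAP 5.2.1 itself makes the Response Evaluable Set primary for tumor response.** This stands in part. For ORR, DCR and CBR, SAP 5.4 agrees with that sentence and departs only from the protocol and from the general Full Analysis Set sentence. It cannot justify the set for OS, nor for the deaths counted in PFS.
- **The specific ORR rule may override the general 5.4 sentence.** If so, ORR is not inflated. The text does not say which governs, and DCR and CBR carry no such rule.
- **The post-baseline evaluation is not said to be a tumor evaluation.** True, and the illustrations assume that it is. It is the likelier reading for a set built for tumor response, and the wording needs tightening either way.
- **SAP 5.4 may not govern every subsection, since FDG-PET has its own set.** FDG-PET is an imaging biomarker with a set named in 5.2.1. OS has no set named anywhere else, so the literal reading of 5.4 applies to it.
- **SAP 7 refers to protocol v1.0 of 07 May 2015, while SAP 3 refers to Amendment 01 of 30 December 2015.** The baseline for the no-change statement is therefore unclear. The conflict between SAP 5.2.1 and 5.4 does not depend on it.
- **The pooled N = 40 response rates are not tables the SAP specifies.** Correct. Rates are summarised by dose group, so the cohort-of-6 example is the closer one and the pooled factors only show scale.
- **Consequence is limited.** Also correct. Efficacy is descriptive, and nothing in the documents shows these tables driving RP2D selection.

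**Conclusion.** The concern holds. On its plain wording SAP 5.4 leaves no efficacy endpoint on the set that both documents call primary for efficacy, and the change is undeclared. The conflict is clearest for PFS and OS.

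If a post-baseline evaluation means a tumor evaluation and SAP 5.4 governs the denominators, DCR, CBR and ORR are overstated whenever at least one subject is dropped and the numerator is not zero. PFS is biased upward to the extent that dropped subjects died before a first scan. OS is biased upward only if dropped subjects died at a higher rate than those retained. How many would be dropped cannot be known from the documents.

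No alpha, power or primary safety analysis is affected. This should be fixed before database lock.

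**What to change.** Amend SAP 5.4 so that ORR, DCR, CBR, PFS and OS are analysed on the Full Analysis Set, with subjects lacking a post-baseline assessment counted as nonresponders and as not disease-controlled. Keep the Response Evaluable Set as a labelled supportive analysis of response rates only. In SAP 5.2.1, remove its designation as primary and say that the required evaluation is a tumor assessment.

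If the sponsor prefers the Response Evaluable Set, SAP 7 must declare and justify the departure from protocol 9.7.1.2, and should name one protocol version consistently with SAP 3.

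The cost is small: edits to the wording of SAP 5.4 and 5.2.1 and one extra supportive table. Reported response percentages become somewhat less favourable if any subject lacks a post-baseline assessment.
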